### **Supportive analysis**

The MMRM of Sensitivity analysis 1 will also be performed in order to provide the LSMEANS (SE) by treatment arm in each subgroup and test the subgroup-by-treatment-by-time point interaction in each pool (A and B) of active arm versus placebo. The MMRM will contain in addition the subgroup variable and the subgroup-by-treatment-by-time point interaction to be tested. When the stratification factor or the % predicted FVC baseline terciles are the subgroups to be tested, the model will not be adjusted on those variables.

In addition, a forest plot will resume the adjusted differences of means (LSMEAN differences) and corresponding 95% CIs of each active arm versus placebo by subgroup.

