4 INTRODUCTION AND RATIONALE

4.1 INTRODUCTION

Idiopathic pulmonary fibrosis (IPF) is a progressive, diffuse, and distinct chronic fibrosing interstitial pneumonia of unknown cause that is uniformly fatal with a median survival of approximately 3 years (1). The clinical course of IPF is variable and not predictable; the rate of decline and progression to death may take several clinical forms: slow physiologic deterioration with worsening severity of dyspnea, rapid deterioration, and progression to death, or periods of relative stability interposed with periods of acute respiratory decline sometimes manifested by hospitalizations for respiratory failure (2). Epidemiological data still qualify IPF as a “rare disease”, even though international studies seem to report an increasing incidence, with current estimates between 4.6 and 16.3 per 100 000 person-years and a prevalence of 13 to 20 cases per 100 000 ((3), (4), (5)). There is a higher predominance of the disease in men (1.5 to 1.7:1) than in women and the frequency increases with age (5). The most important environmental risk factors are cigarette smoking, exposure to metal and wood dust(1), and infectious agents including both viruses and bacteria(6). Genetic transmission occurs in about 0.5% to 3.7% of patients with IPF (7). The diagnosis of IPF often requires a multidisciplinary approach, involving pulmonologists, radiologists, and pathologists experienced in the field of interstitial lung diseases(8). The pathogenic mechanisms are unclear, but a growing body of evidence indicates that the disease is the result of an abnormal behavior of the alveolar epithelial cells that provoke the migration, proliferation, and activation of mesenchymal cells, with the formation of fibroblast and myofibroblast foci. Activated myofibroblasts secrete exaggerated amounts of extracellular matrix molecules with the subsequent destruction of the lung architecture (9). Pirfenidone (Esbriet®, Roche), an oral drug that is hypothesized to inhibit the synthesis of transforming growth factor-beta, was approved so far in Japan, China and in the European Union for the treatment of IPF. Very recently, the FDA approved pirfenidone as well as nintedanib (Ofev®), an oral kinase inhibitor for the treatment of IPF. Per labeling information, these two drugs were shown to significantly reduce the decline of lung function as compared to placebo. No statistically significant effect on death was demonstrated. Lung transplantation is the only therapy that prolongs survival in advanced IPF, although the post-transplantation 5-year survival for patients with IPF is about 48% (10). Interleukin 4 (IL)-4 and interleukin 13 (IL-13) are structurally related cytokines expressed by T helper type 2 lymphocytes and are ligands that share in common at least 1 receptor subunit (IL-4R alpha) (11), (12). Elevations in IL-4 and IL-13 and their receptors have been linked to the pathogenesis of IPF (13), (14). In IPF patients, IL-13 and IL-4 levels in bronchial alveolar lavage fluid are elevated compared to normal controls (15). Such evidence suggests that therapies capable of suppressing or neutralizing these cytokines have the potential for delaying the progression of fibrosis in IPF patients. SAR156597 is an engineered humanized bispecific IgG4 antibody that binds and neutralizes both IL-4 and IL-13. It utilizes an innovative tetravalent bispecific tandem immunoglobulin format to combine the antigen binding domains of an anti-IL-4 antibody and an anti-IL-13 antibody into a single molecule. SAR156597 shows high affinity for IL-4 and IL-13 from both humans and cynomolgus monkeys, and each antibody has binding sites for 2 IL-4 and 2 IL-13 cytokines.

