**Table 4 - primary efficacy outcome algorithm in case of missing data**

Type of missing data	Sensitivity 1	Sensitivity 2
Missing data at week 52 due to reasons other than death or lung transplant	Multiple imputation of week 52 value using copy increment from reference (CIR) approach (assuming normality)	No imputation
Missing data at week 52 due to death	Multiple imputation of week 52 value using the distribution of the last available % Predicted FVC assessment of dead and lung transplanted patients	No imputation
Missing data at week 52 due to lung transplant	Multiple imputation of week 52 value using the distribution of the last available % Predicted FVC assessment of dead and lung transplanted patients	No imputation

**Sensitivity analysis 1:** Assessments at week 52 will be used regardless of whether the patient has previously discontinued treatment.

The absolute change from baseline to week 52 in %predicted FVC will be analyzed on the mITT population using a Mixed Model with Repeated Measures (MMRM) with the fixed categorical effects of treatment arm, stratification factor (with/without Background Therapy), time point, treatment-by-time point interaction, stratification factor-by-treatment-by-time point interaction, as well as the continuous fixed covariate of % predicted FVC baseline. Parameters will be estimated with the Newton-Raphson algorithm, an unstructured covariance matrix will model the within-patient errors, and the denominator degrees of freedom will be estimated using Satterthwaite's approximation.

As for primary analysis, the non-monotone missing patterns with a week 52 value available will not be imputed.

Week 52 missing values (due to reasons other than death or lung transplant) will be imputed using the CIR multiple imputation approach (3). The CIR approach is a multiple imputation methodology based on a Gaussian repeated-measures model:

- First, a large number of datasets will be imputed using the posterior distribution of a linear model containing:
  - baseline value,
  - week 12, week 24 and week 36 time points values (if occurred before the current time point to be imputed),
  - stratification factor,
  - treatment arm\* time point interaction,
  - treatment arm.

This requires a monotone missingness, which is why all time points will be imputed sequentially to determine week 52 value.

- Then, the analysis will be run independently on those imputed datasets to estimate parameters.

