#### 2.4.4.1.2 Subgroups analyses

The following subgroups will be explored:

- Smoking status: Smoke / Never Smoke
- Gender: Male / Female
- Age: Age  $\leq 65$  / Age  $> 65$
- Stratification factor: With / Without background therapy
- % predicted FVC categories at baseline (using terciles: ( $\leq 60$ ,  $> 60$  and  $\leq 75$ ,  $> 75$ ))
- ANA at baseline: Positive / Negative where a Positive ANA titer is defined as titer  $\geq 1:40$

For each subgroup, the change from baseline at 52 weeks in % Predicted FVC will be analyzed using a rank ANCOVA model. For each pool of active arm vs placebo (A and B), the subgroup-by-treatment interaction will be tested as follows:

A) For Smoking status, Gender, Age subgroups: rank ANCOVA model with covariate baseline and terms of treatment, stratification factor, subgroup, treatment-by-subgroup

i. First, compute ranks of baseline and response as in the primary analysis

```
proc rank data=xxx nplus1 ties=mean out=rankdata;  
by stratum;  
var base ranks;  
ranks base_Rank ranks_Rank;  
run;
```

ii. Then, calculate the residuals as in the primary analysis

```
proc glm data=xx;  
by stratum;  
model ranks_Rank=base_Rank;  
output out=residual r=resid;  
run;
```

iii. Finally, the subgroup-by-treatment interaction will be tested using residuals with PROC GLM

```
proc glm data=residual;  
class armn subgroup stratum;  
model resid=stratum armn subgroup subgroup*armn;  
run;
```

B) For Stratification factor subgroup: rank ANCOVA model with covariate baseline and terms of treatment, stratification factor, treatment-by-stratification factor

- i. First, compute ranks of baseline and response without by stratum statement

```
proc rank data=xxx nplus1 ties=mean out=rankdata;  
var base ranks;  
ranks base_Rank ranks_Rank;  
run;
```

- ii. Then, calculate the residuals without by stratum statement

```
proc glm data=xx;  
model ranks_Rank=base_Rank;  
output out=residual r=resid;  
run;
```

- iii. Finally, the subgroup-by-treatment interaction will be tested using residuals with PROC GLM

```
proc glm data=residual;  
class armn stratum;  
model resid=stratum armn stratum*armn;  
run;
```

C) For % predicted FVC baseline categories: rank ANCOVA model with terms of treatment, stratification factor, subgroup, treatment-by-subgroup

- i. First, compute ranks of response as in the primary analysis

```
proc rank data=xxx nplus1 ties=mean out=rankdata;  
by stratum;  
var ranks;  
ranks ranks_Rank;  
run;
```

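### The supportive subgroup MMRM leaves out subgroup-by-time, so its interaction p-value also reacts to subgroups that decline at different rates equally in both arms

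*SAP*

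**What the plan says.** The base model is the MMRM of Sensitivity analysis 1 (SAP 2.4.4.1.1). Its fixed effects are treatment arm and stratification factor, followed by "time point, treatment-by-time point interaction, stratification factor-by-treatment-by-time point interaction, as well as the continuous fixed covariate of % predicted FVC baseline". For the covariance, "an unstructured covariance matrix will model the within-patient errors".

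Under Supportive analysis in SAP 2.4.4.1.2, this model is reused to give LSMeans by arm within each subgroup and to "test the subgroup-by-treatment-by-time point interaction in each pool (A and B) of active arm versus placebo". The terms added are stated in one sentence: "The MMRM will contain in addition the subgroup variable and the subgroup-by-treatment-by-time point interaction to be tested". There is one exception: "When the stratification factor or the % predicted FVC baseline terciles are the subgroups to be tested, the model will not be adjusted on those variables". That exception removes adjustment terms and adds none.

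Neither this section nor the Appendix B summary adds subgroup-by-time or subgroup-by-treatment to the MMRM.

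The subgroups are smoking status, gender, age, background therapy and ANA (two levels each) and baseline % predicted FVC (three levels).

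**The concern.** A three-way interaction isolates treatment heterogeneity over time only if the two-way terms beneath it are in the model. Here treatment-by-time is present, but the two-way terms involving subgroup are not. The three-way term therefore takes up whatever those terms would have explained.

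The two omissions have different consequences:

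- **Subgroup-by-treatment.** Leaving it out moves a component of genuine treatment heterogeneity into the tested term. That alone does not produce a false signal.
- **Subgroup-by-time.** Leaving it out moves a purely prognostic component into the tested term. If one subgroup loses FVC faster than the other by the same amount in both arms, the null hypothesis as specified is false although the drug effect is identical in both subgroups.

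What is at stake is a p-value labelled as a treatment interaction. It could be small because of prognosis, and it would be printed beside a forest plot showing similar treatment effects in the subgroups.

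**Working it through.** **The plan's own figure.** SAP 1.3 gives SD 12, difference 5, two-sided 5% and 80% power, hence 92 per arm. The normal approximation gives 91. Noncentral t gives 92 (power 80.3% at 92 and 79.8% at 91). The figure reproduces, and SD 12 at Week 52 is carried forward.

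**Degrees of freedom of the tested term.** Inputs are two arms per pool, four post-baseline visits (Weeks 12, 24, 36, 52) and 2 or 3 subgroup levels.

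- Two levels: 2 × 2 × 4 = 16 cell means. Time and treatment-by-time span 8, and the subgroup main effect adds 1, so the null model has rank 9. The tested term has 16 − 9 = 7 df.
- Split of the 7: subgroup-by-time (2−1)(4−1) = 3; subgroup-by-treatment (2−1)(2−1) = 1; true three-way (2−1)(2−1)(4−1) = 3.
- Three levels: 24 − (8 + 2) = 14 df, split 6 + 2 + 6.

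Design-matrix ranks confirm 7 and 14, with or without the stratification terms. With both two-way subgroup terms included, the three-way test has 3 df (6 for FVC categories).

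**What does not change.** The model as written and the model with the two-way terms added have equal rank and span the same space of means. Fitted means, LSMeans, LSMean differences and their intervals are therefore identical. Only the hypothesis attached to the three-way term differs.

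**Size of the false rejection (two-level subgroup).** Let the subgroups differ by d points at Week 52 in both arms, with the gap growing linearly: w = (12, 24, 36, 52)/52. There is no treatment heterogeneity. For N patients in the pool and subgroup share p, the noncentrality of the 7-df F test is

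λ = N·p(1−p)·d²·(Dw)′(DΣD′)⁻¹(Dw),

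where D takes successive visit differences and Σ is the visit covariance. The inputs are:

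- From the documents: N = 200 (100 per arm) and SD 12 at Week 52. The share p = 0.66 is the documents' cap on background therapy, used here as the actual share.
- Assumed: SDs 6, 8 and 10 at the earlier visits, AR(1) correlation 0.6, 0.8 or 0.9, linear divergence, complete data, and a 5% level for the interaction test.

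N·p(1−p) = 200 × 0.66 × 0.34 = 44.88. At d = 3, λ = 1.72, 2.36 and 3.28 for the three correlations, and λ scales with d². The rejection rate is P(F(7, 194; λ) > 95th percentile of F(7, 194)), with 194 = 200 patients − 6 mean parameters per visit.

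| Week 52 difference, both arms | corr. 0.6 | 0.8 | 0.9 |
|---|---|---|---|
| 0 points | 5% | 5% | 5% |
| 1 point | 6% | 6% | 6% |
| 2 points | 8% | 9% | 11% |
| 3 points | 12% | 15% | 20% |
| 5 points | 29% | 40% | 55% |

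Under compound symmetry with the same correlations, the rates are 18–30% at 3 points and 49–76% at 5.

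**Simulation check.** This used 2,000 replicates per setting, an estimated unstructured covariance, three other assumed covariance structures, and 50/50 or 75/25 splits. The test as written rejected about 5% at 0 points, 9–12% at 2, 24–41% at 4 and 32–60% at 5. In the same runs, the 3-df three-way test with the two-way terms present, and the joint 4-df test of subgroup-by-treatment plus three-way, stayed at 4–6%.

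**The case against.** **It is only supportive.** This stands, and it limits the point. The leading interaction test in 2.4.4.1.2 is the rank ANCOVA. Its coded models contain their lower-order terms, including a dedicated model for background therapy. (ANA is not named in the coded cases, although the lead-in sentence covers every subgroup.) The Cox subgroup model for disease progression also contains its main effects.

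**It may be shorthand.** The sentence is prose without code, and the base MMRM likewise names stratification-by-treatment-by-time without stratification-by-time. In the base model this is harmless, because that term is an adjustment and is not tested. But the SAP does name lower-order terms elsewhere: treatment-by-time stands beside the three-way term, and the rank ANCOVA code writes out the subgroup main effect with its interaction. A programmer following the sentence literally obtains the 7-df test. If the terms are intended, the SAP should list them.

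**The rates depend on assumptions.** This stands too. They depend on the visit covariance and the prognostic gap, and they use complete data where the plan pools multiply imputed datasets. The larger rates need a 5-point gap, equal to the trial's whole design effect. The df count needs only the four visits.

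Some stronger readings are tempting, but the documents do not support them:

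- *A false signal for background therapy is to be expected.* The Protocol introduction says of pirfenidone and nintedanib that "these two drugs were shown to significantly reduce the decline of lung function as compared to placebo". Those are drug-versus-placebo comparisons. Here background use is not randomised and reflects at least 12 weeks of prior therapy, so treated patients may differ in other ways. A difference in decline is plausible, but its size and direction are not given.
- *The p-value could misdirect the Phase 3 population.* SAP Table 1 ties the Week 52 analysis to the decision to move to Phase 3. No text links a subgroup p-value to the choice of population, and the SAP sets no alpha or decision rule for interaction tests.

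**Conclusion.** The point holds as a narrow specification error. As written, the MMRM interaction test has 7 df (14 for FVC categories), of which 3 (6) measure differing rates of decline irrespective of treatment. A small p-value could not be read as evidence that the drug works differently across subgroups.

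Under the AR(1) assumptions, false rejection runs from about 6% at a 1-point prognostic difference to 29–55% at 5 points, and is higher under compound symmetry. With no prognostic difference the test holds its level. Rates were computed for two-level subgroups only.

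A reader might infer that the subgroup LSMeans or forest plot are biased, or that both missing terms create false signals. Neither follows: the estimates are identical under both models, and only the missing subgroup-by-time term produces the false flag. The primary test and the other subgroup tests are untouched. The change is worth making because it is cheap and the p-value would otherwise be mislabelled.

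**What to change.** In SAP 2.4.4.1.2, Supportive analysis:

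1. Add subgroup-by-time and subgroup-by-treatment to the listed MMRM terms. Subgroup-by-time is essential; subgroup-by-treatment completes the hierarchy.
2. Take the interaction p-value from the Week 52 contrast: the between-subgroup difference in the active-minus-placebo LSMean difference, with 1 df (2 df for FVC categories). This matches the Week 52 primary endpoint. The joint test of subgroup-by-treatment plus three-way (4 df, or 8 for FVC categories) is a valid alternative if heterogeneity at any visit is of interest.
3. State the significance level, or state that the p-value is descriptive.

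The cost is two model terms and one contrast statement. No data or patients are affected, and the LSMeans and forest plot stay as planned.

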#### **2.4.4.2 Analyses of secondary efficacy endpoints**

Secondary efficacy endpoints are described in [Section 2.1.3.2](#) and will be analyzed using the mITT population.

##### *2.4.4.2.1 Disease progression endpoint*

The disease progression will be analyzed on the mITT population. Assessments at week 52 (performed before Day 375) will be used regardless of whether the patient has previously discontinued treatment. Only patients having a baseline and a post-baseline values in at least one time points analysis window for both the % predicted FVC and the % predicted DLCO parameters will be considered in the analysis. No week 52 missing data will be imputed for the disease progression.

The cumulative incidence of disease progression at 52 weeks will be presented graphically by treatment arm and background therapy status, using Kaplan-Meier method. The Kaplan Meier survival estimates (number of patients at risk, number of patients censored, number of disease progression events and probability of surviving without event (95% CI)) will be summarized by time points and overall (number of patients censored, number of events, median time to event).

The censoring reasons will be described by treatment arm and background therapy status.

The time to disease progression at 52 weeks will be tested comparing SAR156597 200 mg qw dose versus placebo using a log-rank test stratified on stratification factor (with/without Background Therapy) at a two-sided type I error level of 5%; and only if this comparison is significant will the SAR156597 200 mg q2w dose be tested versus placebo using a log-rank test stratified on stratification factor (with/without Background Therapy) at a two-sided type I error level of 5%.

The event rates for each of the 3 treatment arms, the hazard ratio and its 90 and 95% confidence interval (CI) compared to placebo for each active arm versus Placebo will be estimated from a

Cox model containing the treatment and the stratification factor variables. The underlying assumption of proportional hazards for Cox model will be checked by visual inspection.

In order to assess the significance, the magnitude and the repartition within components of the treatment effect of disease progression at 52 weeks, the following items will be described by treatment arm and by background therapy status:

- Summary of the disease progression at 52 weeks: number of events, event rates, p-values (only by treatment arm), estimated hazard ratios and their 90 and 95% CIs
- Description of each component as part of the disease progression: their number of events, event rates and their estimated hazard ratios
- Description of each component as individual (all events will be considered meaning that a patient could be represented several times per component): their number of events, event rates, their estimated hazard ratios and their 90 and 95% CIs

In addition, the maximal absolute decrease in % predicted FVC and the maximal absolute decrease in %predicted DLCO will be described by categories ( $\geq 0$  and  $< 5\%$ ,  $\geq 5\%$  and  $< 10\%$ ,  $\geq 10\%$  and  $< 15\%$ ,  $\geq 15\%$  and  $< 20\%$ ,  $\geq 20\%$ ) at 52 weeks. Decomposition of events and maximal events will be explored at 24 weeks as well.

